8.2.4. Adverse Event Summaries

An overall summary of AEs by treatment group and by tumor type as applicable will include the following:

- Number (%) of subjects reporting any TEAEs
- Number (%) of subjects reporting any DLTs
- Number (%) of subjects reporting any SAEs
- Number (%) of subjects reporting any Grade 3 or higher TEAEs
- Number (%) of subjects reporting any TEAEs related to INCAGN01949
- Number (%) of subjects reporting any TEAEs related to nivolumab
- Number (%) of subjects reporting any TEAEs related to ipilimumab
- Number (%) of subjects who temporarily interrupted INCAGN01949 because of TEAEs
- Number (%) of subjects who temporarily interrupted nivolumab because of TEAEs
- Number (%) of subjects who temporarily interrupted ipilimumab because of TEAEs
- Number (%) of subjects who permanently discontinued INCAGN01949 because of TEAEs
- Number (%) of subjects with INCAGN01949 dose reductions because of TEAEs
- Number (%) of subjects who had a fatal TEAE
- Number (%) of subjects who withdrew from study because of an TEAE

The following summaries will be produced by MedDRA term:

- Summary of TEAEs by SOC and PT
- Summary of TEAEs by PT in decreasing order of frequency
- Summary of TEAEs by SOC, PT, and maximum severity
- Summary of Grade 3 or higher TEAEs by SOC and PT
- Summary of INCAGN01949 treatment-related AEs by SOC and PT
- Summary of nivolumab treatment-related AEs by SOC and PT
- Summary of ipilimumab treatment-related AEs by SOC and PT
- Summary of Grade 3 or higher INCAGN01949 treatment-related AEs by PT in descending order of frequency
- Summary of Grade 3 or higher nivolumab treatment-related AEs by PT in descending order of frequency

- Summary of Grade 3 or higher ipilimumab treatment-related AEs by PT in descending order of frequency
- Summary of treatment-emergent SAEs by SOC and PT
- Summary of treatment-emergent SAEs by PT in descending order of frequency
- Summary of treatment-emergent non-SAE by SOC and PT.
- Summary of treatment-related SAEs by SOC and PT
- Summary of TEAEs leading to INCAGN01949 dose reduction by SOC and PT
- Summary of TEAEs leading to INCAGN01949 dose interruption by SOC and PT
- Summary of TEAEs leading to nivolumab dose interruption by SOC and PT
- Summary of TEAEs leading to ipilimumab dose interruption by SOC and PT
- Summary of TEAEs leading to discontinuation of INCAGN01949 by SOC and PT
- Summary of TEAEs leading to death by SOC and PT

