4.3.2. Replacement of Subjects

Subjects may be replaced for any of the following reasons:

- In Phase 1, any subject who withdraws from treatment before the completion of the DLT observation period for any reason other than a DLT (ie, is not evaluable for DLTs; see Section 5.4.2), may be replaced to ensure a minimum number of evaluable subjects.
- [REDACTED]
- Subjects who do not meet the eligibility requirements of the study may be replaced.

Subjects who meet any of the criteria for replacement may remain on study for evaluation as outlined in Section 9.1 and Section 9.2.

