9.1. Study Populations

The full analysis set includes all subjects enrolled in the study who received at least 1 dose of study drug (INCAGN01949). This population will be used in the analyses of demographic, baseline, safety, study drug administration, and efficacy data.

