Additional subjects will be enrolled in a dose cohort to achieve the minimum of 3 evaluable subjects. Depending on treatment group, a subject must receive at least 2 doses of the cohort-specified dose of INCAGN01949, 2 doses of nivolumab, and 1 dose of ipilimumab, or must have had a DLT during the DLT observation period, to be considered evaluable. Subjects who dropout for reasons other than a DLT (eg, events clearly associated with the underlying disease, disease progression, concomitant medication, or comorbidity), during the DLT observation period will result in the subject being nonevaluable and the subject being replaced. Dose modifications should not be made during the DLT observation period without discussion with the medical monitor. The doses of INCAGN01949 to be evaluated in each treatment group are summarized in [Table 1](#).

Table 1: INCAGN01949 Dose Levels and Cohorts

Cohort	Dose of INCAGN01949
-1	2 mg
1	7 mg
2	20 mg
3 (Starting Dose)	70 mg
4	200 mg
5	350 mg
6	700 mg

Note: A higher starting dose of INCAGN01949 was chosen based on safety data from the monotherapy study (INCAGN 1949-101).

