5.3. Analysis Populations

5.3.1. Full Analysis Set

The FAS includes all subjects enrolled in the study who received at least 1 dose of INCAGN01949, nivolumab, or ipilimumab. The nivolumab FAS population includes all subjects in the FAS population who received at least 1 dose of nivolumab administered in mg or mg/kg. The ipilimumab FAS population includes all subjects in the FAS population who received at least 1 dose of ipilimumab.

Table summaries, unless otherwise indicated, will be provided by treatment group and tumor type-specific cohorts.

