8.2. Adverse Events

8.2.1. Adverse Event Definitions

A TEAE is any AE either reported for the first time or worsening of a pre-existing event after first dose of study drug. For the subjects in the FAS population, analysis of AEs (as discussed below) will be limited to TEAEs, but data listings will include all AEs regardless of their timing in relation to study drug administration.

Adverse events will be tabulated by MedDRA PT and SOC. Severity of AEs will be graded using the National Cancer Institute CTCAE. The CTCAE version 4.03 is used for this study. The CTCAE reporting guidelines and grading details are available on the Cancer Therapy Evaluation Program website.

The subset of AEs considered by the investigator to be related to INCAGN01949, nivolumab, or ipilimumab will be considered to be treatment-related AEs and will be summarized. If the investigator does not specify the relationship of the AE to study drug, the AE will be considered to be treatment-related. The incidence of AEs and treatment-related AEs will be tabulated. In addition, SAEs will also be tabulated.

A grading (severity) scale is provided for each AE term. If the toxicity is not included in the CTCAE v4.03 criteria, it will be rated on a scale of 1 to 5 as follows: 1 = mild, 2 = moderate, 3 = severe, 4 = life-threatening, and 5 = death related to AE. All toxicities will be graded based on the worst level reached, not the level they may have reached if they had not been treated. When the intensity of an AE changes over time for a reporting period (eg, between visits), each

change in intensity will be collected as an AE until the event resolves. Only the worst grade will be reported in AE summaries. Also, the Grade 3 or higher AEs will be summarized.

Any missing onset date, causality, or severity must be queried for resolution. Unresolved missing causality and severity will be handled according to the following rules:

- An unresolved missing causality will be considered treatment-related.
- An unresolved missing severity will be identified as an unknown severity.

For purposes of analysis, all AEs will be considered TEAEs unless the AE can unequivocally be defined as not treatment-emergent.

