3.2 Adverse Events				
3.2.1.1	Overall Summary of Treatment-Emergent Adverse Events – by Treatment Group and Dose	Phase 1 FAS Population	X	X
3.2.1.2	Overall Summary of Treatment-Emergent Adverse Events – by Treatment Group and Tumor Type	Phase 2 FAS Population	X	X
3.2.2.1	Summary of Treatment-Emergent Adverse Events by MedDRA System Organ Class and Preferred Term – by Treatment Group and Dose	Phase 1 FAS Population	X	
3.2.3.1	Summary of Treatment-Emergent Adverse Events by MedDRA System Organ Class and Preferred Term – by Treatment Group and Tumor Type	Phase 2 FAS Population	X	
3.2.4.1	Summary of Treatment-Emergent Adverse Events by MedDRA Preferred Term in Decreasing Order of Frequency – by Treatment Group and Dose	Phase 1 FAS Population	X	X
3.2.4.2	Summary of Treatment-Emergent Adverse Events by MedDRA Preferred Term in Decreasing Order of Frequency – by Treatment Group and Tumor Type	Phase 2 FAS Population	X	X
3.2.5.1	Summary of Treatment-Emergent Adverse Events by MedDRA System Organ Class, Preferred Term, and Maximum Severity – by Treatment Group and Dose	Phase 1 FAS Population	X	
3.2.5.2	Summary of Treatment-Emergent Adverse Events by MedDRA System Organ Class, Preferred Term, and Maximum Severity – by Treatment Group and Tumor Type	Phase 2 FAS Population	X	
3.2.6.1	Summary of Grade 3 or Higher Treatment-Emergent Adverse Events by MedDRA System Organ Class and Preferred Term – by Treatment Group and Dose	Phase 1 FAS Population	X	X
3.2.6.2	Summary of Grade 3 or Higher Treatment-Emergent Adverse Events by MedDRA System Organ Class and Preferred Term – by Treatment Group and Tumor Type	Phase 2 FAS Population	X	X
3.2.7.1	Summary of Any INCAGN01949 Treatment-Related Adverse Events by MedDRA System Organ Class and Preferred Term – by Treatment Group and Dose	Phase 1 FAS Population	X	X
3.2.7.2	Summary of Any INCAGN01949 Treatment-Related Adverse Events by MedDRA System Organ Class and Preferred Term – by Treatment Group and Tumor Type	Phase 2 FAS Population	X	X
3.2.8.1	Summary of Any Nivolumab Treatment-Related Adverse Events by MedDRA System Organ Class and Preferred Term – by Treatment Group and Dose	Phase 1 Nivolumab FAS Population	X	X

Table No.	Title	Population	Standard	In-Text
3.2.8.2	Summary of Any Nivolumab Treatment-Related Adverse Events by MedDRA System Organ Class and Preferred Term – by Treatment Group and Tumor Type	Phase 2 Nivolumab FAS Population	X	X

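### The planned DLT percentage uses all dosed Phase 1 subjects as its denominator, while the 3 + 3 + 3 and MTD-exceeded rules use DLT-evaluable subjects, so replaced subjects dilute the tabulated rate

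*SAP*

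**What the plan says.** The reported rate. SAP 8.2.4 lists "Number (%) of subjects reporting any DLTs" among the rows of the overall adverse event summary. SAP 8.2.1 sets the population: "For the subjects in the FAS population, analysis of AEs (as discussed below) will be limited to TEAEs". In Appendix A the matching Phase 1 output is Table 3.2.1.1, "Overall Summary of Treatment-Emergent Adverse Events – by Treatment Group and Dose", whose population column reads Phase 1 FAS. SAP 5.3.1 defines that set: "The FAS includes all subjects enrolled in the study who received at least 1 dose of INCAGN01949, nivolumab, or ipilimumab". The full analysis set in Protocol 9.1 likewise takes in everyone given at least one dose of INCAGN01949.

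The decision rule. SAP 3.1.1 and Protocol 4.1.1 escalate, expand or stop on DLTs among 3, 6 or 9 evaluable subjects. A subject qualifies by receiving the required doses "or must have had a DLT during the DLT observation period, to be considered evaluable". Dropping out during the period for a reason other than a DLT "will result in the subject being nonevaluable and the subject being replaced". Protocol 4.3.2 adds: "Subjects who meet any of the criteria for replacement may remain on study for evaluation as outlined in Section 9.1 and Section 9.2".

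The legible part of SAP 5.3 defines the FAS, its nivolumab and ipilimumab versions, and the response evaluable population. None is a DLT-evaluable set. SAP 8.2.2 and Listing 2.6.3 list DLTs without a denominator.

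**The concern.** The same quantity has two denominators. A DLT in the observation period makes a subject evaluable by definition, and Protocol Table 8 also counts missing planned doses because of toxicity as a DLT. The subjects who are dosed and then replaced are therefore those without a DLT in the period. On the FAS they count as DLT-free, although they were not observed as the rule requires.

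What is at stake is the reported rate. Evaluating DLTs and defining the recommended dose is the Phase 1 primary objective, and Protocol 9 says only Phase 1 will be analysed. A cohort that exceeded the MTD at exactly one-third could appear in the study report below one-third.

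A related problem concerns Groups C and E. Protocol 5.4.2 sets a DLT period only for Groups A, B and D, to study Day 28. Table 3.2.1.1 covers the whole Phase 1 FAS, and SAP 5.2 says data are summarised overall as well as by group. A 0% for Group C or E would not be an observed DLT rate, and those subjects would dilute any overall column.

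**Working it through.** **Inputs.** Evaluable cohort sizes of 3, 6 and 9 and the stopping results (2 or more of 3, 3 of 6, 3 of 9) come from SAP 3.1.1; the one-third threshold is in the MTD definition there. The number of dosed but replaced subjects, k, is not given; 0 to 3 per cohort is assumed.

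**Step 1: reproduce SAP Table 3.** Let a0 = (1−p)³ and a1 = 3p(1−p)², the probabilities of 0 and 1 DLT in 3 evaluable subjects. Escalation follows 0/3, 1/6 or 2/9:

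P(escalate) = a0 + a1·a0 + a1²·a0.

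At p = 0.20: 0.512 + 0.384×0.512 + 0.384²×0.512 = 0.512 + 0.197 + 0.075 = 0.784. At p = 0.30, 0.40, 0.50 and 0.60 the formula gives 56.1%, 35.0%, 18.9% and 8.8%. All five values match SAP Table 3, so its figures rest on evaluable denominators.

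**Step 2: the dilution.** With x DLT subjects among n evaluable,

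tabulated rate = x/(n+k) = (x/n) × n/(n+k).

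One replaced subject multiplies the rate by 3/4 = 0.75, 6/7 = 0.86 or 9/10 = 0.90 for n = 3, 6 or 9. If k = 0 or x = 0 the two rates agree.

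**Step 3: every result that exceeds the MTD.**

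| Evaluable result | k = 0 | k = 1 | k = 2 | k = 3 |
|---|---|---|---|---|
| 3/9 | 33.3% | 30.0% | 27.3% | 25.0% |
| 4/9 | 44.4% | 40.0% | 36.4% | 33.3% |
| 5/9 | 55.6% | 50.0% | 45.5% | 41.7% |
| 3/6 | 50.0% | 42.9% | 37.5% | 33.3% |
| 4/6 | 66.7% | 57.1% | 50.0% | 44.4% |
| 2/3 | 66.7% | 50.0% | 40.0% | 33.3% |
| 3/3 | 100% | 75.0% | 60.0% | 50.0% |

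In this range only 3/9 falls below one-third, and one replaced subject is enough.

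**Step 4: how often 3/9 arises.** It needs one DLT in each of three successive triplets, so P(3/9) = a1³. Dividing by 1 − P(escalate) gives its share of cohorts that exceed the MTD.

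| True DLT rate | P(3/9) | Share of MTD-exceeding cohorts |
|---|---|---|
| 20% | 5.7% | 26.2% |
| 30% | 8.6% | 19.5% |
| 40% | 8.1% | 12.4% |
| 50% | 5.3% | 6.5% |

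At true rates of 5% and 10%, P(3/9) is only 0.25% and 1.4%. These figures do not include the chance that the same cohort also had a replaced subject, which the documents do not allow to be computed.

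**Step 5: the numerator.** SAP 8.2.2 identifies a DLT by a flag on the adverse event form for protocol-defined DLTs. The observation period therefore enters only through Protocol 5.4.2. If an event outside the period were flagged, a 2/9 cohort (22.2%) could read 3/9 (33.3%).

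**The case against.** The strongest reply is that the FAS is the planned set for safety data (Protocol 9.1, SAP 8.2.1) and that this row is one line of a descriptive overview. Escalation is settled in cohort reviews (Protocol 5.4.5), and Protocol 9.3 plans no formal tests. The count is printed beside the percentage, and a reader could largely rebuild the evaluable denominator from the DLT, drug administration and disposition listings. Nothing in the documents shows a cohort that exceeded the MTD: Protocol 1.2.5 reports no monotherapy DLTs, and Protocol 1.5.3 describes the combinations as generally well tolerated up to 350 mg.

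Most of this stands. It limits the consequence, but it does not make the FAS a suitable denominator for an outcome that requires an observed period.

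Four further limits also stand:

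- A reader might infer that the error can only be downward. Dilution by replaced subjects can only lower the rate, but a flagged out-of-period event would raise it.
- A reader might infer that Protocol 4.3.2 itself places replaced subjects in the DLT denominator. It points to Section 9.2 as well as 9.1, and 9.2 counts evaluable subjects. The denominator follows from SAP 8.2.1, SAP 5.3.1 and Table 3.2.1.1.
- The sentence defining the MTD speaks of subjects in a cohort without saying evaluable; the operative rule in the same section does say it.
- Table 3.2.1.1 is marked as a standard table. The standard table conventions, the sample displays, the DMC Charter and any text removed after SAP 5.3.2 were not available and could contain a different rule, including how Groups C and E are printed.

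**Conclusion.** The mismatch is real and affects reporting. The plan names a denominator for the DLT percentage that differs from the one its escalation and MTD-exceeded rules use, and each dosed, replaced subject lowers the tabulated rate of any cohort with a DLT. With 1 to 3 replaced subjects (assumed), a 3/9 cohort reads 30.0% to 25.0% instead of 33.3%. With none replaced, or no DLT, there is no difference for that cohort.

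Two stronger readings are not supported. One is that dose decisions are biased; they rest on evaluable subjects, and the overview row does not itself document the MTD decision. The other is that this is the only DLT rate anywhere in the plan. It is the only DLT percentage among the legible planned study-report tables, but SAP 9.1.1 also has the DMC review a DLT rate, with no denominator stated.

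The change is worth making because the quantity belongs to the Phase 1 primary objective and the criteria are already written. Confidence is moderate, given the material that was not available.

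**What to change.** - Define a DLT-evaluable set in SAP 5.3 from the existing SAP 3.1.1 criteria, for Groups A, B and D.
- Report DLT n/N (%) by treatment group and dose on that set, for events in the Protocol 5.4.2 period.
- Mark the DLT row not applicable for Groups C and E, and leave them out of any overall DLT percentage.
- List nonevaluable subjects with reasons, and list any flagged out-of-period events separately.

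The other adverse event rows stay on the FAS. The cost is one population definition, one changed table row and one short listing. The doses received, DLT flag and event dates needed for this are already collected.

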8.3. Clinical Laboratory Tests

8.3.1. Laboratory Value Definitions

Laboratory values and change from baseline values will be summarized descriptively by visit. Baseline will be determined according to Section 4.1.3. If there are multiple values that meet the criteria for baseline, additional rules may be provided after consultation with the medical monitor to delineate which value will be defined as baseline.

Laboratory test values outside the normal range will be assessed for severity based on CTCAE grade or similar criteria where clinical intervention is required for CTCAE grading. The incidence of abnormal laboratory values and shift tables relative to baseline will be tabulated.

8.3.2. Laboratory Value Summaries

All test results and associated normal ranges from local laboratories will be reported in SI units. All tests with numeric values will have a unique unit per test. Any laboratory test results and associated normal ranges from local laboratories will be converted to SI units. For the limited number of cases where the associated normal ranges from a local laboratory cannot be obtained despite due diligence, if query is unsuccessful at resolving the issue and analysis is mandatory, then the clinical scientist and medical monitor can provide a suitable normal range to be used in determining CTCAE grading and flags for above and below normal.

When there are multiple laboratory nonmissing values for a subject's particular test at a scheduled visit, the laboratory value with the smallest laboratory sequence number will be used in by-visit summaries (Table 8).

Table 8: Identification of Records for Postbaseline By-Visit Summaries

Priority	Laboratory Visit	Proximity to Visit Window	Tiebreaker
1	Scheduled	In-window	Use smallest laboratory sequence number
2	Unscheduled	In-window	
3	Scheduled	Out-of-window	

Numeric laboratory values will be summarized descriptively in SI units, and non-numeric test values will be tabulated when necessary. In addition, line graphs and box-and-whisker plots will be provided for hemoglobin, platelet counts, WBCs, and neutrophils.

For test results that will be summarized with available normal ranges, the number and percentage of subjects with the laboratory values being low (but never high), normal, high (but never low), and both low and high will be calculated for each test. This shift summary will be produced for each test for the FAS population. The denominator for the percentage calculation will use the number of subjects in the baseline category (ie, low, high, normal, missing) as the denominator for the percentage in each of the categories during the treatment period.

In cases where differentials of hematology parameters are obtained without corresponding absolute count data, efforts will be made to investigate if the conversion to an absolute value will lead to additional abnormalities. This will be discussed with the clinical team regarding appropriate documentation and action.

8.4. Vital Signs

Values at each scheduled visit, change, and percentage change from baseline for vital signs, including systolic blood pressure, diastolic blood pressure, pulse, respiration rate, and body temperature, will be summarized descriptively.

Criteria for clinically notable vital sign abnormalities are defined in [Table 9](#). The abnormal values for subjects exhibiting clinically notable vital sign abnormalities will be listed along with their assigned treatment group. Alert vital signs are defined as an absolute value outside the defined range and percentage change $> 25\%$ from baseline. The abnormal values for subjects exhibiting alert vital sign abnormalities will be listed.

Table 9: Criteria for Clinically Notable Vital Sign Abnormalities

Parameter	High Threshold	Low Threshold
Systolic blood pressure	> 155 mmHg	< 85 mmHg
Diastolic blood pressure	> 100 mmHg	< 40 mmHg
Pulse	> 100 bpm	< 45 bpm
Temperature	$> 38^\circ\text{C}$	$< 35.5^\circ\text{C}$
Respiratory rate	$> 24/\text{min}$	$< 8/\text{min}$

8.5. Electrocardiograms

Twelve-lead ECGs including heart rate, PR, QRS, QT, QTcF, QTcB, JTC, and RR intervals will be obtained for each subject at the screening, EOT, and safety follow-up visits during the study. Values at each scheduled visit, change, and percentage change from baseline will be summarized for each ECG parameter. Baseline will be determined as the average of all nonmissing values before the first administration of INCAGN01949, nivolumab, or ipilimumab.

Criteria for clinically notable ECG abnormalities are defined in [Table 10](#). Subjects exhibiting clinically notable ECG abnormalities will be listed with study visit and assigned treatment group. Abnormal values for subjects with alert ECG values, defined as both the absolute value and the percentage change from baseline being outside normal ranges, will be identified and listed.

Table 10: Criteria for Clinically Notable Electrocardiogram Abnormalities

Parameter	High Threshold	Low Threshold
QTcF	> 460 msec	< 295 msec
PR	> 220 msec	< 75 msec
QRS	> 120 msec	< 50 msec
QT	> 500 msec	< 300 msec
RR	> 1330 msec	< 600 msec

QTcF = Fridericia correction.

9. INTERIM ANALYSES

9.1. Overview of Interim Analyses

9.1.1. Interim Analyses for Safety

There will be no planned, formal interim analyses for the Phase 1 dose escalation portion of the study. The review of accrued clinical data will be conducted by Incyte and provided to study investigators via teleconferences at the end of Phase 1 of the study. Based on review of the most current safety data, the sponsor (in consultation with the study investigators and using the dose-escalation/de-escalation rules) will determine if and at what dose additional subjects should be treated in the study.

A DMC will be charged with evaluating interim safety results. The DMC will be composed of members who are internal to the sponsor but not members of the study team. The DMC members will include a medical monitor who will serve as the DMC chair and meeting facilitator, the head of biostatistics or a designee, the head of regulatory affairs or a designee, and the study medical monitor who will be a nonvoting member. The DMC will meet at least every 6 months starting after the first 10 subjects have been dosed to review the rate of DLTs and irAEs in each treatment group and the overall safety of the subjects treated with INCAGN01949, nivolumab, and ipilimumab. Additional operational details of the interim analyses, including TFLs provided to the DMC, will be provided in the DMC Charter. Additional safety analyses may be performed at the discretion of the DMC chair.

[figure not shown]
